[contact]

Email: [contact]

Funder

CW+ Charity (Chelsea and Westminster Hospital NHS Foundation Trust) and Bristol Myers Squibb Pharmaceuticals Ltd are funding this study.

This protocol describes the ALMA-AF trial and provides information about procedures for entering participants. Every care was taken in its drafting, but corrections or amendments may be necessary. These will be circulated to investigators in the study. Problems relating to this study should be referred, in the first instance, to the Principal Investigator.

This study will adhere to the principles outlined in the UK Policy Frame Work for Health and Social Care Research It will be conducted in compliance with the protocol, Data Protection Act 2018 and General Data Protection Regulations (Europe) and other regulatory requirements as appropriate.

Keywords

Atrial fibrillation, Screening, Machine learning

LIST OF ABBREVIATIONS

Define all unusual or 'technical' terms related to the trial. Add or delete as appropriate to your trial. Maintain alphabetical order for ease of reference.

ΑE Adverse Event ΑF Atrial fibrillation AR **Adverse Reaction** CI **Chief Investigator ECG** Electrocardiogram **Good Clinical Practice GCP ICF** Informed Consent Form

International Standard Randomised Controlled **ISRCTN**

Trials Number

Machine learning ML

Machine learning algorithm **MLA**

NHS R&D National Health Service Research &

Development

ы **Principal Investigator**

PIC **Participant Identification Centre PIS Participant Information Sheet PPG Photoplethysmography** QA **Quality Assurance Quality Control** QC

Qualified Person QP

REC Research Ethics Committee Serious Adverse Event SAE SAR **Serious Adverse Reaction SDV Source Data Verification** SOP **Standard Operating Procedure**

SSI **Site Specific Information**

SUSAR Suspected Unexpected Serious Adverse

Reaction

STUDY SUMMARY

TITLE Application of machine learning algorithm to identify patients at highest

risk of atrial fibrillation (AF) for targeted screening

DESIGN Prospective cohort study

AIMS To evaluate the potential benefit of using our machine learning

algorithm to aid AF screening.

To compare the use of different health technologies for AF screening

To evaluate the optimal duration and frequency of rhythm monitoring

for AF screening

OUTCOME MEASURES Detection of atrial fibrillation

Diagnostic yield of machine learning algorithm for detection of AF

POPULATION Primary care patients in Hounslow community

SAMPLE SIZE ~ 9 000 high risk AF patients identified from machine learning algorithm

~ 1 800 patients for further AF screening

ELIGIBILITY Inclusion criteria

Aged 18 years old or above

Identified as high-risk for AF by our machine learning algorithm

Access to smartphone depending on allocated screening group

Exclusion criteria

Have already a diagnosis of atrial fibrillation prior to study enrolment

Below the age of 18 years old

Presence of cardiac electronic implantable device

DURATION 1.5 years

STUDY FLOW CHART

[figure not shown]

Figure 1 Study Design

1. INTRODUCTION

Atrial fibrillation (AF) is the most common heart rhythm disturbance (arrhythmia). Individuals with atrial fibrillation have a five-fold increased risk of developing strokes. AF can be persistent or paroxysmal (intermittent). People with AF can be unaware that they have the condition as they may not display any symptoms. This results in many people presenting with AF at the time they present to hospital with a stroke. Strokes are debilitating, cause significant permanent disability and are a burden to the healthcare system.

If AF is identified earlier, strokes can be prevented with treatment in the form of a blood thinner (known as anticoagulation). In order to make a diagnosis, a heart tracing called an electrocardiogram (ECG) will be required. Currently, over 100 individuals will need to be screened in order to pick one individual with AF. However, a new machine learning algorithm has been developed (using previous AF risk score models and primary care data) and it has been predicted to increase our yield in identifying patients at risk of developing atrial fibrillation. Early data has suggested that it reduces the number needed to screen to 9 to pick one patient with atrial fibrillation.

We will run this machine learning algorithm on the databases of general practices in the Hounslow area. Once the high-risk AF individuals have been identified, they were cluster randomised to four groups according to their general practice. Individuals from four groups will be invited to be screened for AF. Individuals from each group without a diagnosis of AF will be invited to receive a health technology to aid AF detection.

There has been a recent surge in the number of technologies available for ECG monitoring. As more people have smartphones, this provides us with more opportunities to monitor patients for longer and more frequently and ultimately, diagnose AF earlier. There have been no comparative trials of mobile health technologies. This study will allow them to be compared for the first time.

The ability of the machine learning algorithm and different health technologies to detect AF will be analysed. Due to the paroxysmal nature of AF, we will also use health technologies to determine the optimal duration and frequency of rhythm monitoring for AF screening as this is currently unknown.

2. STUDY OBJECTIVES

AIMS

- 1. To evaluate the potential benefit of using our machine learning algorithm to aid AF screening
- 2. To compare the use of different health technologies for AF screening
- 3. To evaluate the optimal duration and frequency of rhythm monitoring for AF screening

3. STUDY DESIGN

This will be a 1.5-year study in which participants will be recruited prospectively from databases of 46 general practices (GPs) in the Hounslow area. Our machine learning algorithm will be used on these databases to identify our participants. Our participants will be identified as those at risk of developing atrial fibrillation. The practices will be cluster randomised into 4 groups. The high- risk AF individuals will be invited for screening for AMLA-AF protocol, version 1.1 25/10/21, IRAS Project ID: 293493

AF. The four groups are as follows: (1) ECG group (2) Holter monitoring group, (3) a Photoplethysmography (PPG) monitoring group and (4) a long term AliveCor monitoring group.

All individuals who have agreed to participate in the study will be screened initially once with a single lead ECG recording using an AliveCor device. This will be done either at their general practice or a research clinic at West Middlesex University Hospital. Any individual found to have AF will be followed up by their general practice to receive appropriate treatment. They will also not be required to have any further screening.

After this initial screening, if an individual has not been found to have AF and belongs to groups 2-4, they will undergo further screening for a period of 3 months. This will be based on their allocated group. They will be able to take their screening technology home. Again, if any individual is found to have AF, they will be followed up by their general practice to receive appropriate treatment.

Participation in this study will be entirely voluntary and will not affect participants' current or future care. Participants will be free to withdraw from the study at any time without having to provide a reason. Participants will be recruited prospectively from general practices, on a first-come first-serve basis, to minimise bias. Recruitment will continue throughout the study.

Data collected from participants prior to drop out or loss to follow-up will be included in the data analysis. We are not aware of any ongoing studies that are competing for the same group of participants or whose results may affect recruitment. Similarly, our study will not jeopardise other studies either.

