5. STUDY PROCEDURES AND RANDOMISATION

Prior to patient recruitment, the machine learning algorithm will be run centrally at NHS Hounslow Clinical Commissioning Group, Hounslow House. It will be run across 46 general practice databases in the Hounslow area, which includes an estimated population of 315 000 people.

The algorithm will generate an anonymised list of high- risk AF individuals with their associated general practice. It is expected that this will be approximately 9 000 people.

Each general practice will be clustered into three different sets depending on the size of the population of high- risk AF patients found at that practice. The sets are classed into large (>200 patients identified screen), medium (100-200 patients) and small (< 100 patients). This will allow the GP practices to be later cluster randomised into four groups corresponding to the different screening strategies, with roughly equal number of large/medium/small GP practices in each group. These four groups that we will compare are: (1) ECG group, (2) holter monitoring group, (3) a PPG monitoring group and (4) a long term AliveCor monitoring group.

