5.1 RECRUITMENT

Following this, each general practice will be visited separately and the algorithm will be run at each individual practice to identify individual high-risk AF patients. A member of each general practice will be shown how to run the algorithm and will run it on the database of the general practice. High-risk AF participants will be invited to be recruited into the study by a member of the general practice team. Every effort will be made to recruit vulnerable adults who lack capacity so they can be recruited if they wish to be involved. All high -risk participants recruited will be registered and flagged up on a depersonalised health data set covering the North West London (NWL) population, known as the Discover dataset, which is the NWL health research cohort register. This will allow the retrieval of health care data of these participants while keeping their anonymity. Each participant will have an anonymous identifier number. Approval for this has been sought from NWL Data Access Committee.

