8. STATISTICS AND DATA ANALYSIS

It is estimated that 9 000 participants will be identified to be high risk for AF. Taking into account the dropout from previous screening exercises, we estimate that 1 800 (20%) participants will belong to the four groups.

The diagnostic yield for AF detection will be analysed for the machine learning algorithm and each health technology.

There will be selective analysis of the data collected from the monitoring groups to determine the optimal frequency and duration.

For each participant for the holter monitoring group, two rhythm histories will be created. The first rhythm history will just include the results of 72hr monitor. The second rhythm history will include the results of first 24hrs of the 72hr monitor, the results of the second 24hr monitor and the third 24hr monitor. This will allow the screening strategies of 3 x24hr monitoring and 1 x 72hr monitoring to be compared. The diagnostic yield of AF detection for the two strategies will be compared.

The data from the PPG and long term AliveCor monitoring groups will then be selectively analysed with some recordings blanked from analysis to compare the diagnostic yield of different durations (1-month vs 3 months) and different frequencies (Daily vs alternate days vs weekly).

Data analysis will be performed at West Middlesex University Hospital.

All high-risk AF patients will be followed up for the detection of AF. This will be at least 1 year from the last recruited patient.

The end of the study will be defined as last followup required for the purposes of the study.

Data and all appropriate documentation will be stored for a minimum of 10 years after the completion of the study, including the follow-up period.

AMLA-AF protocol, version 1.1 25/10/21, IRAS Project ID: 293493

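### First-come first-served enrolment of volunteers after practices are allocated does not minimise bias: the technology comparison is open to differential uptake, and the one-off ECG yield describes attenders only

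*Protocol*

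**What the plan says.** Section 3 gives the recruitment rule and its reason: "Participants will be recruited prospectively from general practices, on a first-come first-serve basis, to minimise bias". The same section says "Participation in this study will be entirely voluntary".

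The order of steps comes from sections 1, 5 and 5.1. The algorithm is run centrally, practices are grouped by the size of their high-risk list and randomised to four screening strategies, and each practice is then visited and runs the algorithm itself. After that, "High-risk AF participants will be invited to be recruited into the study by a member of the general practice team".

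Section 8 expects a list of about 9 000 and a much smaller enrolled sample: "we estimate that 1 800 (20%) participants will belong to the four groups". The study summary and section 4.1 make smartphone access a condition of entry in the PPG and long term AliveCor groups only.

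Two statements bear on who is followed up. Section 8: "All high-risk AF patients will be followed up for the detection of AF". Section 5.1: "All high -risk participants recruited will be registered and flagged up on a depersonalised health data set".

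**The concern.** Taking people in the order they come forward is neither a random nor a consecutive sample of the list. It selects on willingness and readiness to respond, and nothing in the rule offsets that.

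The selection also happens after allocation, and the groups are not offered the same thing: a single ECG; three periods of Holter or patch recording; or recordings twice a day for three months. Part of the differential selection is written into the entry criteria, since a person without a smartphone can enter the ECG or Holter group but not the other two. Where the smartphone criterion applies, the group has to be known when eligibility is judged.

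Two aims are exposed. For aim 2, a difference in yield between technologies could come from who enrolled rather than from the device. For aim 1, the yield is measured in the fifth of the list that attends, while the algorithm is meant to be judged on everyone it flags.

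**Working it through.** **Inputs.** High-risk list 9 000, expected participants 1 800 and uptake 20% (section 8); 46 practices (section 5); four groups (section 3); number needed to screen of 9 from early data (section 1).

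**The plan's own figure.** 9 000 × 0.20 = 1 800, which reproduces. The remaining 9 000 − 1 800 = 7 200 (80%) contribute nothing to the primary endpoint or the technology yields. On average this is 9 000/46 ≈ 196 listed and 1 800/46 ≈ 39 enrolled per practice. With an even split (assumed) there are 1 800/4 = 450 per group.

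**Order of steps.**

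| Step | Section | Protected by randomisation? |
|---|---|---|
| Central run gives an anonymised list by practice | 5 | Yes, precedes allocation |
| Practices randomised, balanced on list size | 1, 3, 5 | – |
| Local run and invitation by practice staff | 5.1 | No, follows allocation |
| Smartphone criterion in two of four groups | Summary, 4.1 | No, differs by group |
| Voluntary enrolment, about 20% | 3, 8 | No |
| Baseline single-lead ECG, the same in all groups | 3, 7 | Measured in enrolled people only |

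**Illustration 1: yield in the whole list.** Let y = 1/9 be the AF rate in attenders and k the ratio of the rate in non-attenders to that in attenders. The value of k is an assumption; the protocol gives none. List yield = 0.2y + 0.8ky.

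- k = 0.5: 0.0222 + 0.0444 = 6.7%, number needed to screen 15
- k = 1: 0.0222 + 0.0889 = 11.1%, number needed to screen 9
- k = 1.5: 0.0222 + 0.1333 = 15.6%, number needed to screen 6.4

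With no assumption about the unseen 80%, the bounds run from 0.2y = 2.2% to 0.2y + 0.8 = 82.2%.

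**Illustration 2: comparison between groups.** Suppose the lists have equal AF rates, one group's volunteers show 1/9, and another's show a multiple of it (assumed). Take 450 v 450, a two-sided 5% test and no allowance for clustering.

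| Ratio | Yield in second group | Spurious difference | Probability of rejecting |
|---|---|---|---|
| 0.7 | 7.8% | −3.3 points | 40% |
| 0.8 | 8.9% | −2.2 points | 20% |
| 1.25 | 13.9% | +2.8 points | 24% |
| 1.5 | 16.7% | +5.6 points | 67% |

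A test that allows for clustering would reject less often, but the spurious difference would be the same size.

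**How far the common baseline ECG can check this.** At 1/9 and 450 per group, the standard error of a difference is √(2 × 0.1111 × 0.8889/450) = 0.021, so a 95% interval is about ±1.96 × 0.021 = ±4.1 points, and wider with clustering. Three of the four differences above would fall inside it. The check is worthwhile but imprecise.

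**The case against.** The strongest reply is that the selection comes from voluntary participation, which no consented screening study avoids, and not from the first-come rule. This largely stands. A reader might infer that the rule itself picks out the 20%. The document does not support that: the figure is expected uptake based on earlier screening exercises, no cap on enrolment is stated, and recruitment stays open throughout. The sentence may have been meant to limit staff discretion over whom to enrol. It still does not deliver what it claims.

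Other stronger readings also fail:

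- *The primary yield is invalid.* The one-off ECG is the same in every group and precedes any group-specific monitoring. Yield per person screened is a valid description of attenders. What is missing is a basis for extending it to the list.
- *All three aims are compromised.* Aim 3 compares monitoring schedules within the same participants' recordings, so differential uptake between groups does not confound it.
- *All recruiters and invitees know the group.* The protocol does not say so. It follows for the two smartphone groups; elsewhere it is inferred from the order of steps.
- *Volunteers are fitter, or more symptomatic.* The document says nothing on this, so no direction of bias can be claimed.
- *Sections 5.1 and 8 flatly contradict each other.* Section 5.1 says who is flagged for data retrieval, not that others cannot be followed. The follow-up population is unclear rather than provably inconsistent.

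Analyses such as uptake by group are commonly left to a statistical analysis plan, which is not shown. Their absence is not the finding. The finding is that the protocol credits the design with a property it lacks.

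**Conclusion.** The statement that first-come first-served recruitment minimises bias is wrong and should go. Enrolment is voluntary, follows practice allocation, covers about 20% of the list, and uses an entry criterion that differs by group. The technology comparison of aim 2 may therefore be biased by differential uptake. The algorithm's yield of aim 1 is sound for attenders but cannot be assumed to represent the list. Aim 3 is not affected by between-group selection.

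Neither the size nor the direction of the bias can be derived from the protocol. The range of 15 to 6.4 for the list-wide number needed to screen rests wholly on the assumed ratio of 0.5 to 1.5, and on carrying the early figure of 1 in 9 over to this study's attenders. The rejection probabilities rest on assumed ratios, an even split and no clustering. They show that modest differences in uptake could matter, not that they will occur.

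**What to change.** 1. In section 3, delete the claim about bias. In sections 3.1 and 8, state that yields refer to attenders.
2. Report uptake and baseline characteristics by randomised group, including AF on the common baseline ECG.
3. For the technology comparison, add a sensitivity analysis that restricts every group to smartphone holders. This requires smartphone access to be recorded at baseline in the ECG and Holter groups too.
4. Reconcile section 5.1 (recruited participants flagged) with section 8 (all high-risk patients followed up).
5. Use the section 8 follow-up for a supporting comparison of newly recorded AF over about 12 months across the full high-risk lists, by randomised practice group and allowing for clustering. Depersonalised or practice-level counts would suffice for non-participants. The window fits the minimum of one year that section 8 already plans.

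The first four items cost wording and one baseline item. The fifth may need a small extension of the data access, which section 5.1 describes for recruited participants. Its contrast is also diluted: at 20% uptake, an assumed difference of 5 points among attenders becomes 0.20 × 5 = 1 point on the list if non-attenders are unaffected. It therefore supports the per-attender yield and does not replace it.

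Two apparent remedies should not be pursued. With no cap, inviting people in random order would leave who consents largely unchanged. The central list is anonymised, so it cannot itself be used to fix whom each practice invites.

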4.3 WITHDRAWAL CRITERIA

Participants will be withdrawn from the study if they fulfil one of the following:

- a) Unable to use their screening health technology
- b) Withdrawal of consent
- c) Presence of cardiac electronic implantable device

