7. SCREENING AND FOLLOWUP

Participants' care will continue under their normal clinical or healthcare teams. Therefore, their followup will be arranged by and conducted by these team(s).

Following recruitment into the study, each participant will be invited for screening for AF at their practice or a research clinic at West Middlesex University Hospital.

At the baseline assessment, each participant will be required to have a single lead ECG recording for a minimum of 30 seconds using an AliveCor device (two metal pads on a plastic strip, Figure 2) and smartphone which will be provided by the research team. Figure 3 demonstrates the use of the device with a smartphone. For a recording, at least 1 finger is required to rest on each of the metal pad (electrodes). If AF is identified from this recording, the patient will be referred back to their practice for appropriate treatment.

Figure 2: AliveCor device

[figure not shown]

Figure 3: AliveCor recording

Participants without a diagnosis of AF in the holter monitoring group, photoplethysmography (PPG) monitoring group and the long term AliveCor monitoring group will be given a health technology to take away. They will have monitored with this technology for 3 months. The technology that they receive will be based on the monitoring group they belong to. The ECG group will not have any further monitoring.

For the holter monitoring group, the participants will receive a 72-hr holter monitor/ECG patch initially, and two further 24-hr holter monitors/ ECG patches at 6 and 12 weeks. These will be returned to the research team following completion of each monitoring period.

For the Photoplethysmography (PPG) monitoring group, the participants will be given access to a smartphone application called Fibricheck to use on their own smartphone. The participant will be provided with a QR code to scan for the prescription of 3- month

monitoring period. The participant will need to download the Fibricheck App on their own smartphone from the App store. They will then need to scan the QR code with the Fibricheck App. The participant will then be able to start making recordings by placing their finger on the camera for 1 minute. Figure 4 demonstrates how to set the Fibricheck App on a smartphone and Figure 5 shows how to take a recording with the App.

[figure not shown]

Figure 4: How to set up Fibricheck App on smartphone

[figure not shown]

Figure 5: How to take a recording using the Fibricheck App

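### Holter comparison (72 h versus 3 x 24 h): losses after the first monitor shorten only the 3 x 24 h history, so its yield is understated if missed monitors count as no AF

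*Protocol*

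**What the plan says.** Protocol section 3 gives a general rule for incomplete participation: "Data collected from participants prior to drop out or loss to follow-up will be included in the data analysis".

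Section 7 sets the Holter schedule: "the participants will receive a 72-hr holter monitor/ECG patch initially, and two further 24-hr holter monitors/ ECG patches at 6 and 12 weeks".

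Section 8 fixes the Holter comparison. On who is included: "For each participant for the holter monitoring group, two rhythm histories will be created". On the first history: "The first rhythm history will just include the results of 72hr monitor". On the second: "The second rhythm history will include the results of first 24hrs of the 72hr monitor, the results of the second 24hr monitor and the third" 24-hour monitor. The yields of the two strategies are then compared.

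For the PPG and AliveCor groups, section 8 says the data will be "selectively analysed with some recordings blanked from analysis to compare the diagnostic yield of different durations (1-month vs 3 months") and of different recording frequencies.

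The protocol expects some incomplete monitoring. One withdrawal criterion in section 4.3 is "Unable to use their screening health technology", and section 9.2 lets the practice clinician substitute other monitoring while the participant stays in the analysis. No section says how an incomplete history is counted or limits these comparisons to complete histories.

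**The concern.** The two Holter strategies are constructed from the same people, so randomisation cannot balance losses between them. The 72 h history is finished when the first monitor comes back. The 3 x 24 h history depends on two more monitors, at 6 and 12 weeks. Any loss in between shortens only the second history. If the missing hours are scored as no AF, the comparison mixes how well the pattern detects AF with how many people stayed in this trial.

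The result could not be read as real-world adherence to 3 x 24 h either. Everyone had already worn 72 hours before being asked for the later monitors, which a true 3 x 24 h programme would not require.

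At stake is part of aim 3, the optimal duration and frequency of monitoring, which the introduction calls currently unknown.

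**Working it through.** **Inputs.** From the protocol: 9,000 identified, 1,800 participants, four groups, and the monitor schedule. All yields, wear rates and monitoring-phase dropout rates below are assumptions, because the protocol gives none.

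**1. The plan's own figure.** 0.20 x 9,000 = 1,800, as stated. Equal groups (assumed) would give 1,800 / 4 = 450. The dropout mentioned there concerns the step from identified patients to participants, not the three months of monitoring.

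**2. Hours in each history.**

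| Participant | 72 h history | 3 x 24 h history |
|---|---|---|
| All monitors worn | 72 of 72 | 72 of 72 |
| Lost after first monitor | 72 of 72 | 24 of 72 |
| Misses week 12 only | 72 of 72 | 48 of 72 |
| First monitor off after 24 h, later ones worn | 24 of 72 | 72 of 72 |

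The loss is one-sided for anyone lost after the first monitor. The last row shows that it can run the other way.

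**3. Illustration A.** Assume the first 24 h yields 2.0%, each later day of the 72 h block adds 1.0 point, and each spaced 24 h adds 1.3 points.
- True yields: 72 h = 2 + 2 x 1.0 = 4.0%; 3 x 24 h = 2 + 2 x 1.3 = 4.6%.
- 80% and 65% wear the later monitors: 2 + 1.45 x 1.3 = 3.885%. Mean hours = 24 + 24 x 1.45 = 58.8.
- 90% and 80%: 2 + 1.70 x 1.3 = 4.21%.
- The ranking reverses only if the two wear rates sum to less than 2 / 1.3 = 1.54.
- In 450 people, the fall from 4.6% to 3.885% is about 3.2 people. The reversed gap of 4.0 - 3.885 = 0.115 points is about half a person.

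**4. Illustration B.** Let d be the share lost after the first monitor. Observed 3 x 24 h = (1 - d) x true 3 x 24 h + d x first-24 h yield, and the 72 h yield is unchanged.
- True 1.5% (24 h), 3% (72 h), 4% (3 x 24 h): d = 20% gives 0.8 x 4 + 0.2 x 1.5 = 3.5%; d = 40% gives 3.0%, a tie with 72 h.
- Both strategies truly 3%: d = 20% gives 2.7% against 3.0%, a spurious deficit.

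**5. One month versus three.** Let d1 and d2 be the shares dropping out in month 1 and in months 2-3, each on average mid-interval. Observed Y1 = Y1 x (1 - d1/2). Observed Y3 = observed Y1 + (Y3 - Y1) x (1 - d1 - d2/2). With true yields of 3% and 5%:
- d2 = 20% only: 3.0% and 3.0 + 2.0 x 0.9 = 4.8%. The increment falls from 2.0 to 1.8 points.
- d1 = 20% only: 2.7% and 2.7 + 2.0 x 0.8 = 4.3%. Both fall, and the increment is 1.6 points.
- One month is nested in three, so observed Y3 cannot fall below observed Y1.

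**6. Would a completer set plus everyone who stopped for AF repair it?** Use illustration A per 100 people at 80%/65% wear, with the 65% within the 80%, no overlap between cases, and people with AF found stopping.
- AF-free throughout: 100 - 4 - 1.3 - 1.3 = 93.4.
- Kept: 4 + 0.80 x 1.3 + 0.65 x 1.3 + 0.65 x 93.4 = 4 + 1.04 + 0.845 + 60.71 = 66.6.
- 72 h: 4 / 66.6 = 6.0%. 3 x 24 h: 3.885 / 66.6 = 5.8%.

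The ratio is unchanged and both yields are inflated, so this set does not remove the bias.

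**7. Does detection among those who wore each monitor repair it?** Same figures, with wear unrelated to AF and 98 people free of AF in the first 24 h.
- Week 6: 1.04 / (0.80 x 98) = 1.04 / 78.4 = 0.01327.
- Week 12: 0.845 / (0.65 x (98 - 1.3)) = 0.845 / 62.855 = 0.01344.
- Cumulative: 1 - 0.98 x (1 - 0.01327) x (1 - 0.01344) = 4.6%, the assumed true value.

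**The case against.** The strongest reply is that the bias is inferred. Section 3 says only that data gathered before dropout are used. It does not say that missing monitoring counts as AF-free, and censoring at the last recording would also comply with it. Rules for incomplete monitoring often sit in a SAP, which is not shown here. This stands in part. The direction of the bias is conditional on how missed monitors are scored. But section 8 does fix that every Holter participant enters both histories, and followed as written that gives unequal hours.

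A reader might also infer more than the documents support:
- **That only the spaced or longer strategy ever loses data.** Early removal or failure of the first monitor shortens the 72 h history, and dropout in month 1 lowers both the 1-month and the 3-month yield.
- **That the duration ranking could reverse.** Nesting rules this out; only the increment shrinks. For PPG and AliveCor, fading use may also be a real part of a 3-month strategy, because these participants did what such a programme asks.
- **That missed monitors are unrelated to AF.** Participants may leave without giving a reason, so this is an assumption.
- **That a reversal of the Holter ranking is likely.** It depends on assumed yields and wear rates, and at 90%/80% wear it does not occur.

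**Conclusion.** The point holds in a limited form, mainly for the Holter comparison. The written rules give participants lost after the first monitor a full 72 h history and a partial 3 x 24 h history. If missed monitors are scored as no AF, the 3 x 24 h yield is too low relative to 72 h. In the illustrations the effect runs from a narrowed advantage (4.6% observed as 4.2%) through a tie to a slight reversal (3.9% against 4.0%). The true size cannot be derived from the protocol.

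For 1 versus 3 months the consequence is milder: an understated added yield, in the illustration 2.0 points observed as 1.8 or 1.6.

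The primary endpoint in section 3.1, detection with a one-off ECG, is not touched. This is a cheap improvement to a secondary comparison, not a flaw in the trial's main result.

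**What to change.** In section 8:

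1. **Holter.** Estimate each strategy's cumulative detection from the monitors actually worn. For 3 x 24 h, combine detection in the first 24 h with detection at the week-6 and week-12 monitors among those who wore them and had no AF earlier in that strategy's history. Inverse-probability weighting of participants with both later monitors is an alternative. Do not use a completer set that adds back everyone who stopped for AF. State separately how people whose AF was found on days 2-3 of the first monitor are counted in the 3 x 24 h history, since they are not ordinary dropouts.
2. **One month versus three.** Report cumulative detection with ordinary dropouts censored at their last recording. This fits the time-to-first-detection outcome already in section 3.1.
3. **Alongside.** Report the all-participants yield, labelled as delivered, and the hours analysed per strategy.

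The cost is analysis wording only, since monitors are returned and recordings submitted to the team under section 7. The downsides are slightly less precision and an assumption that dropout is unrelated to undetected AF. The as-delivered result does not test that assumption, but it shows how much the answer depends on the handling of dropouts.
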